#### **3.2.3 Exploratory Endpoints**

Exploratory endpoints will include changes from baseline in the systemic markers of inflammation: D-dimer, cardiac troponin, C-reactive protein [CRP], lactate dehydrogenase [LDH] and ferritin.

#### 3.2.4 Safety Endpoints

The safety and tolerability endpoints will include reported AEs, laboratory tests, vital signs, ECG, physical examinations, concomitant medications and hospitalization.

Hospitalization endpoints will include days of hospitalization and status of supplementary oxygen requirement at discharge (No/Yes). When calculating days of hospitalization, if a subject dies while hospitalized, the number of days of hospitalization will be imputed as the worst maximal duration of 42 days.

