## **8 STUDY POPULATION**

The study population will consist of patients diagnosed with COVID-19 infection who have developed pneumonia defined as radiographic opacities on chest X-ray, and require supplemental oxygen. The patients must be hospitalized at least during screening and at baseline (Day 1).

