#### **3 STUDY DESIGN**

### 3.1 General Design and Study Schema

This is a phase 2a, proof of concept, multi-center randomized double-blind, parallel arm, placebo controlled study.

After informed consent is obtained, patients will enter a screening phase for no more than 3 days, to determine eligibility.

[figure not shown]
Approximately 40 eligible patients will be randomized to receive either opaganib added to standard of care, or matching placebo added to standard of care, in a randomization ratio of 1:1. Patients will be stratified based on a minimization algorithm, as specified in section 3.4. Treatment assignments will remain blinded to the patient, investigator and hospital staff, as well as the sponsor. As there is currently no consensus for a definitive treatment specifically targeting the SARS-CoV-2 virus causing COVID-19 (K. Wilson, 2020), standard of care will refer to regional, institutional or physician directed therapies, that may be implemented during the COVID-19 pandemic.

Study participants will receive either opaganib 2 x 250 mg capsules (500 mg) every 12 hours, or matching placebo, in addition to standard of care (pharmacological and/or supportive). Study drug will be administered every day for 14 days (Day 1 to Day 14), unless the patient has been discharged from the hospital without requiring supplemental oxygen, in which case study drug will only be administered to Day 10.

All participants will be followed up for 4 weeks after their last dose of study drug, which may occur at the end of the 2-week double-blind treatment phase or after premature study drug discontinuation, based upon patient or physician determination.

The maximum duration of study participation will be 45 days (including up to 3 days screening; 2 weeks double-blind (DB) phase and 4-weeks off-study drug follow-up).

The study schema is presented below and Visit-specific procedures and assessments are outlined in Table 1.

Off-study drug follow-up starts when study drug is stopped per protocol or after discontinuation per patient or physician decision

Assessments	Screening	Randomizatio n	DB	Phase	Early termination	Safety follow-up
	Days -3 - 1	Day 1	Day 7	Day 14	termination	ionow up
ICF signed	X					
Inclusion/exclu sion criteria	X					
Demographics; medical and surgical history	X					
Review concomitant medication(s) 	X	X	X	X	X	X
Review of adverse events 		X	X	X	X	X
Physical examination 	X		X	X	X	X

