#### **3.2 Study Endpoints**

#### 3.2.1 Primary efficacy endpoint

The primary efficacy objective of the study is to evaluate the effect of Opaganib on total supplemental oxygen requirement (area under the curve) using daily oxygen flow (L/min) measurements for 14 days (Day 1 to Day 14).

The primary efficacy endpoint will calculate for each patient the area under the curve of the supplemental oxygen requirement through day 14, using the trapezoidal rule after subtracting the baseline oxygen requirement at each day.

The following rules will be applied:

- If several values of oxygen requirement (L/min) are recorded in a certain day, then for the primary analysis the highest of these values will be taken.
- Days where no supplementary oxygen was needed, will be recorded as 0.
- Subjects who require intubation and mechanical ventilation, at these days will be assigned the maximal supplemental oxygen flow requirement of 8L/min (or if higher, the maximal value observed in the study).
- For subjects discharged from hospital without requiring supplemental oxygen prior to Day 14, the oxygen requirement (L/min) will be assigned thereafter as 0 for each day to Day 14 (in the rare case that subject will re-hospitalize before Day 14, the new supplemental oxygen data will be collected and used, until day 14).
- For the primary analysis, if a patient dies any time before Day 14), all his/her values (D1-D14) will be assigned at the maximal supplemental oxygen flow requirement of 8L/min, or if higher, the maximal value observed in the study.

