For patients discharged from hospital with supplemental oxygen prior to Day 14, or early terminate the treatment before Day 14 while still requiring supplemental oxygen, data on the supplemental oxygen up to Day 14 is expected to be collected. However, in the rare case that all supplemental oxygen values are missing after discharge/treatment discontinuation, the individual AUC will be calculated where the last value is carried forward - until Day 14, or death, if occurred before (note, death event is analyzed as specified above). This approach will be employed also if a patient initiates new investigational therapy for COVID-19 within 14 days, in which case the primary analysis will include only measurement taken under study treatment while the rest of the days will be imputed as noted above. Sensitivity analysis will address this scenario as well. To note, according to blinded data review prior to database lock, no cases of such prohibited investigational therapy was recorded.

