### 5.4 Handling Withdrawals and Missing Data

Missing data in the primary endpoint are handled as described in sections 3.2.1 and 7.2. Sections 3.2.2 and 7.3 provides details on handling missing data for the secondary efficacy endpoints. Generally, no imputation will be performed for safety endpoints unless stated otherwise in the specific endpoint analysis. For time to event analysis, early withdrawal (or death before event of interest) will be addressed via right censoring, as described in Sections 3.2.2.

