### 6.4 Covid-19 Disease Information

Disease information will be summarized by treatment group and overall using ITT, mITT and Safety populations. Summaries will be presented with descriptive statistics as specified in section 5.1 above

- Reason for hospitalization
- Time from onset of symptoms to Hospitalization (Days)
- Time from onset of symptoms to diagnosis (Days)
- Time from onset of symptoms to randomization (Days)
- Time from diagnosis to hospitalization (Days)
- Time from diagnosis to supplemental oxygen (Days)
- Time from diagnosis to randomization (Days)
- Time from hospitalization to supplemental oxygen (Days)

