## 8.11 Hospitalization

Summary statistics on subject's hospitalization information will be provided. These will include duration of hospitalization and whether the subject is taking supplemental oxygen at discharge.

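### The hospital-days summary gives the worst value only to deaths in hospital, so a patient who dies elsewhere after discharge is scored like a survivor discharged on the same day

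*SAP*

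**What the plan says.** SAP 3.2.4 lists days of hospitalization among the safety endpoints and gives one rule for death: "if a subject dies while hospitalized, the number of days of hospitalization will be imputed as the worst maximal duration of 42 days". SAP 5.4 sets the default for everything else in the safety data: "Generally, no imputation will be performed for safety endpoints unless stated otherwise in the specific endpoint analysis". SAP 8.11, which describes the summary, adds no rule: "These will include duration of hospitalization and whether the subject is taking supplemental oxygen at discharge".

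Three further things are left unstated: the day from which hospital days are counted, whether a readmission adds to the count, and what a survivor still in hospital at the end of follow-up receives.

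The study calendar is in SAP 3.1: "The maximum duration of study participation will be 45 days (including up to 3 days screening; 2 weeks double-blind (DB) phase and 4-weeks off-study drug". The last of these periods is follow-up, and its four weeks run from each patient's last dose. A patient discharged without needing oxygen is dosed only to Day 10.

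The SAP expects discharges during the treatment period. Section 3.2.1 has a rule that begins "For patients discharged from hospital with supplemental oxygen prior to Day 14", and it also provides for readmission, "in the rare case that subject will re-hospitalize before Day 14".

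**The concern.** A patient may leave hospital and die at home within study follow-up. The worst value does not apply, because the death did not occur in hospital, and no other imputation applies either. The patient enters the table with a completed stay, exactly as a survivor discharged on the same day does. An arm in which discharges were followed by deaths would look better on this measure than an arm in which the same patients died in hospital.

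This differs from how the SAP treats death elsewhere. In SAP 3.2.1 a patient who dies before Day 14 receives the maximal oxygen value on every day, with no condition on place. In SAP 3.2.2, time to 50% oxygen reduction and the two swab endpoints censor deaths at the end of follow-up as the unfavourable result. The oxygen-free proportion counts death as failure, and both intubation endpoints count death as an event. Hospital days takes over the worst-value idea but makes it depend on where the patient died, and no reason is given.

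SAP 5.3 says the results will be read from the overall pattern of benefit, so a descriptive table can still influence the reading.

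**Working it through.** **Inputs**
- Worst value: 42 days, in-hospital deaths only (SAP 3.2.4).
- Calendar: up to 3 days of screening, 14 days of treatment, 28 days of follow-up after the last dose (SAP 3.1).
- Planned arm size: 20 (SAP 3.3).
- Length of the stay before a death after discharge: not in the documents. Assumed values are 5, 7, 10 and 14 days.

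**1. Reproduce the plan's figure.** 14 + 28 = 42, the span from Day 1 to the end of follow-up when the last dose is on Day 14. Adding screening gives 3 + 14 + 28 = 45, the stated maximum participation. The value 42 therefore fits a count that starts on Day 1.

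**2. Trace a death after discharge.** Take a patient discharged on Day 5 who dies at home on Day 8. The rule in 3.2.4 is not met. Under the 5.4 default nothing is imputed. Counted from Day 1, the score is 5, the same as for a survivor discharged on Day 5. Had the patient been readmitted and died in hospital, the rule would have been met and the score would be 42. The gap is confined to deaths outside hospital.

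**3. Size per death.** Scoring such a death as its observed stay *s* instead of 42 lowers the arm mean by (42 − *s*)/20.

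| Assumed stay *s* (days) | 42 − *s* | Arm mean lower by (days) |
|---|---|---|
| 5 | 37 | 1.85 |
| 7 | 35 | 1.75 |
| 10 | 32 | 1.60 |
| 14 | 28 | 1.40 |

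**4. Does follow-up reach Day 42 for everyone?** With a last dose on Day 10, follow-up ends at 10 + 28 = Day 38. It ends sooner for patients who stop earlier. A corrected rule cannot assume that all days to Day 42 are observed.

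**5. Is 42 for any death the same as days alive and out of hospital to Day 42?** No. The patient in step 2 was alive and out of hospital on Days 6 and 7, about 2 days. With the same Day 5 discharge and death on Day 40, the figure is about 34 days (Days 6 to 39). Assigning 42 hospital days implies 0 in both cases, so the two measures rank patients differently.

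**The case against.** The strongest defence is that an in-hospital death cuts a stay short, so its observed length misleads, whereas a discharged patient's stay is complete and correctly recorded. Adding later deaths turns a duration into a composite. The SAP's statement that death is the highly unfavourable outcome (section 10) is made for efficacy endpoints, and hospital days is listed under safety. This has some force: no stated principle is broken. But by assigning 42 to in-hospital deaths the SAP has already made the measure a composite of stay and death, and only the condition on place remains unexplained.

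The second defence is low materiality, and it stands. The table is descriptive, no formal inference is planned (SAP 3.3, 5.3), and the median is reported alongside the mean (SAP 5.1). Deaths are visible elsewhere: Day 30 mortality, Kaplan-Meier curves of time to death, adverse event tables by fatal outcome, and listings.

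A reader might also infer three stronger points that the documents do not support:
- *A long-stay survivor can score above the 42 given to a death.* This happens only if days are counted from admission or screening. With 3 hospital days before Day 1, a survivor in hospital through Day 42 would score 3 + 42 = 45. The SAP does not state such an origin, and 42 = 14 + 28 points to Day 1, from which no survivor can exceed 42 within follow-up.
- *Every patient brings hospital days from before Day 1.* Protocol 8 requires hospitalization during screening and at baseline, but Protocol 12.1.2 allows screening on Day 1 itself.
- *Readmission days are excluded.* The hospital-days text does not mention readmission. That is silence, not exclusion.

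**Conclusion.** The point holds for deaths outside hospital after discharge. As written, SAP 3.2.4 and 5.4 together score such a patient like a survivor discharged on the same day, which is inconsistent with how the SAP handles death in its primary endpoint and most secondary endpoints. Each such death makes the mean of a 20-patient arm about 1.4 to 1.85 days lower than scoring it 42 would. That range rests on assumed stays of 14 to 5 days and on the planned arm size. The number of such deaths cannot be estimated from the documents and may be zero.

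The counting origin and the handling of readmission are missing details to be filled in, not demonstrated errors. Severity is minor.

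**What to change.** Amend SAP 3.2.4, with a cross-reference in 8.11, to state that:
- days in hospital are counted from Day 1, the origin that 14 + 28 = 42 implies;
- days of any readmission during study follow-up are included;
- 42 days are assigned to any death during study follow-up, wherever it occurs;
- days after a patient's own follow-up has ended are handled by a named rule, or a common earlier end day is used for everyone, with the worst value reset to match it. Day 30, already the mortality horizon, is one candidate: four weeks of follow-up reach it for any last dose on Day 2 or later (2 + 28 = 30);
- a survivor still in hospital at the end of the window receives the days observed in that window.

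The measure should not be described as equivalent to days alive and out of hospital.

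The cost is a few lines of SAP text and a small derivation from admission, discharge and death dates. Readmission dates must be available on the eCRF. The remaining burden is the choice of end day or of a rule for unobserved days, because patients dosed only to Day 10 are followed to about Day 38 and earlier stoppers for less.

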# 3.3 Sample Size and Power Considerations

It is planned to enroll approximately 40 eligible patients into the double-blind treatment phase, to receive either opaganib added to standard of care (n=20), or matching placebo added to standard of care (n=20). The sample size for this Proof of Concept study was not chosen for statistical consideration, as there are no formal statistical inferences planned. The size of the study is judged adequate for the preliminary evaluation objectives.

# 3.4 Randomization and Blinding

A total of 40 subjects 18 to 80 years old, inclusive will be randomized, using a 1:1 assignment ratio, to treatment with either Opaganib 500 mg Q12 hour (20 subjects) or Placebo (20 subjects), respectively.

A dynamic randomization using the minimization method will be used in this study by Bioforum's DM vendor. Three stratification factors will be used for the minimization algorithm:

- 1. Age at screening,  $\geq 70$  years of age, (yes or no)
- 2. HbA1c at screening,  $\geq 6.5$ , (yes or no);
- 3. Oxygen requirement at baseline, requiring non-invasive positive pressure ventilation (e.g. via PEEP, BIPAP, CPAP, HFNC), (yes or no)

The minimization algorithm will be programmed by Bioforum Ltd using Viedoc system and will employ the Pocock and Simon (Pocock S.J. and Simon R. 1975) methodology with biased coin probability of 0.8 and 'Range' as the variation method. All stratification factors will use the same weight of importance. If the subject meets the eligibility criteria, he or she will be allocated to Opaganib 500 mg Q12 hour or Placebo at 1:1 ratio respectively. Once the enrollment of the subject is approved, the investigator will assign the subject an ID number (subject number) provided by the Viedoc system after running the algorithm on the subject's stratification information.

Treatment assignments will remain blinded to the patient, investigator and hospital staff, as well as the sponsor.

# 3.5 Sequence of Planned Analyses

#### 3.5.1 Interim Analyses

No formal interim analysis to stop the study early is planned for this proof of concept study.

#### 3.5.2 Final Analyses and Reporting

All final, planned analyses identified in this SAP will be performed only after the last patient has completed the study. The randomization codes will not be unblinded until this SAP has been signed and approved. Any exploratory analyses completed to support study analyses, which were not identified in this SAP, will be documented and reported in appendices to the CSR. The analysis of the primary endpoint and supporting efficacy secondary analyses can be started once this SAP has been signed, all data up to day 14 (including) has been locked and unblinded. Study personnel involved in data management activities and those engaged in study conduct will remain blinded until the few remaining safety follow-up visits will be performed and all remaining unlocked data (after Day 14) have been cleaned and locked. Only then, formal final analysis for the CSR will be performed. No difference is expected in results of the primary endpoint (and supporting efficacy secondary endpoints noted above), however in case of any difference occur, it will be documented and presented in the CSR as well. Procedures and firewalls have been defined and documented in study files to maintain study integrity during the partial team unbinding.

# 4 ANALYSIS POPULATIONS

This section describes the analysis populations defined for the study.

### 4.1 Screened

The Screened population will include all subjects who underwent screening.

# 4.2 Intention to Treat (ITT)

The ITT population will include all randomized subjects. In this population, treatment will be assigned based upon the treatment to which patients were randomized regardless of which treatment they actually received.

# 4.3 Safety

The safety population will include all randomized patients who receive at least one dose of study medication. In this population, treatment will be assigned based upon the treatment patients actually receive regardless of the treatment to which they were randomized.

# 4.4 Modified ITT (mITT)

This population consists of all subjects that were randomized and treated with at least one dose of study drug. In this population, treatment will be assigned based upon the treatment to which subjects were randomized regardless of which treatment they actually received.

# 4.5 Per protocol (PP)

A per protocol population will include those subjects in the mITT population who had no major protocol violation. Criteria for PP protocol will be mainly based on inclusion and exclusion criteria and will be defined before database lock. The list of protocol deviations

precluding patients from PP population has been prepared using blinded review and documented in study files.

# **5 GENERAL ASPECTS FOR DATA ANALYSIS**

### 5.1 General

Descriptive statistics for continuous variables include n, mean, standard deviation, standard error of the mean, median, minimum, and maximum.

Descriptive statistics for categorical variables include patient counts and percentages.

Summaries of clinically significant abnormal values will include all post baseline values (including scheduled, unscheduled, and early termination visits).

All data collected will be presented in the by-subject data listings, sorted by subject and by time point, where appropriate.

If departures from these general conventions are present in the specific evaluation sections of this SAP, then those will take precedence over the above general conventions.

# 5.2 Specification of Baseline Values

In general, Baseline will be defined for each subject as the last available, valid, nonmissing assessment before first study drug dose.

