#### **3.2.2** Secondary Efficacy Endpoints

The secondary efficacy endpoints are as follows:

1. Time to 50% reduction from baseline in supplemental oxygen based on oxygen flow in L/min

This endpoint will be based on the oxygen flow values used for the primary efficacy endpoint. It will be calculated as the number of days from baseline (Day 1) of study

Statistical Analysis Plan	RedHill Biopharma
Version: 3, Date: 13-DEC-2020	Study ABC-110

medication until the first day when the subject reached a value, which is at least 50% lower than the baseline value (the event of interest). Patients who early terminate the study before reaching this reduction will have their time censored at the last valid observation time point. Patients who will die within the followup timeframe will be censored at the time of the end of the follow-up period, thus taking the highly unfavorable possible outcome for this endpoint. The time frame for this endpoint is from Day 1 until end of off-study-drug followup. Additional analysis will be performed in the time frame of the 14-day-treatment DB Phase period (sensitivity analysis).

To note, in order to focus this endpoint on sustained success, it implies increase in supplemental oxygen negating initial success would be followed for re-achievement of success. Further note, a patient who reached success but did not have any further data supporting this success (i.e. discharged from hospital still requiring oxygen and no further data supporting success afterwards), may be subject to sensitivity analysis where regarded censored at last evaluable time.

2. The percentage of patients no longer receiving supplemental oxygen for at least 24 hours by Day 14

This endpoint will be defined per subject as a binary ("Success" / "Failure") variable with "Success" indicating that a subject no longer receiving supplemental oxygen for at least 24 hours by Day 14, and "Failure" otherwise. Patients who will die within 14-days will be regarded as "Failure", corresponding to the highly unfavorable possible outcome.

To note, in order to focus this endpoint on sustained success, it implies need in supplemental oxygen negating initial success would be followed for re-achievement of success.

3. The time to two consecutive negative swabs for SARS-CoV-2 by PCR, at least 24 hours apart

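### Baseline oxygen defaults to a single last pre-dose reading while study days with several readings use the highest, so within-arm improvement is understated and the 50% reduction is harder to reach, by the same rule in both arms

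*SAP*

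**What the plan says.** - **Baseline.** SAP 5.2 gives one rule for all variables, introduced as a general one: the "last available, valid, nonmissing assessment before first study drug dose". SAP 5.1 lets specific sections override general conventions, but neither SAP 3.2.1 nor SAP 3.2.2 defines baseline oxygen, so the default applies.
- **Study days.** SAP 3.2.1 has a rule for any day with more than one flow reading: "then for the primary analysis the highest of these values will be taken". Protocol 17.3 has the same rule and is also silent on how baseline oxygen is chosen.
- **Primary endpoint.** The AUC is formed "using the trapezoidal rule after subtracting the baseline oxygen requirement at each day".
- **Oxygen-free days.** "Days where no supplementary oxygen was needed, will be recorded as 0".
- **Secondary endpoint 1.** SAP 3.2.2: "This endpoint will be based on the oxygen flow values used for the primary efficacy endpoint". The event is the first day with a value "which is at least 50% lower than the baseline value".
- **Day 1.** SAP 3.2.2 and 8.5 label baseline as Day 1. Nothing says whether Day 1 readings taken before the first dose count towards the Day 1 maximum.
- **Reading frequency.** Footnote 1 to the schedule of assessments asks for daily recording in hospital. It does not say how many readings a day.

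**The concern.** The highest of several readings is, on average, above a single reading. A patient whose need never changes, measured several times a day, therefore scores a positive baseline-adjusted AUC where the answer should be zero. The same patient must bring the day's peak down to half of an unselected single reading to count as a 50% reduction.

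What is at stake is the descriptive output. The trial plans no formal inference (SAP 3.3) and will be read by its overall pattern of benefit (SAP 5.3). SAP 7.2 reports each group's mean AUC with a 95% confidence interval. SAP 7.3 reports Kaplan-Meier medians and 14-day cumulative incidence of the 50% reduction by group. A reader will take these as change from baseline, and the mismatch moves them in a known direction. None of the analyses in SAP 7.2.1 (missing data, covariate adjustment, per protocol, ranks) varies the baseline rule or the highest-value rule.

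**Working it through.** The plan states no SD, effect size or power, so there is no figure of its own to reproduce. From the documents: the two rules above, Days 1 to 14, and 20 patients per arm (SAP 3.3). Assumed: the number of readings per day (k), the within-day SD (s) and the shape of within-day variation.

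**1. Weight of baseline.** A trapezoid over 14 daily values has 13 unit intervals, so subtracting a constant b from each day subtracts 13b from the AUC. Changing only the baseline rule moves a patient's AUC by exactly 13 x (highest pre-dose reading - last pre-dose reading).

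**2. Upward shift, closed form.** For a patient on oxygen on all 14 days, shift = 13 x d(k) x s, where d(k) is the expected excess of the highest of k readings over one reading, in SD units. With normal readings and s = 1 L/min:

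| k | d(k) | shift (L/min-days) |
|---|---|---|
| 1 | 0 | 0 |
| 2 | 0.564 | 7.3 |
| 3 | 0.846 | 11.0 |
| 4 | 1.029 | 13.4 |

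Ends of the assumed range, normal readings:
- k = 2, s = 0.5: 13 x 0.564 x 0.5 = 3.7
- k = 6, s = 1.5: 13 x 1.267 x 1.5 = 24.7

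For right-skewed (shifted exponential) readings, d(k) = 1/2 + ... + 1/k:
- k = 2, s = 0.5: 13 x 0.5 x 0.5 = 3.3
- k = 6, s = 1.5: 13 x 1.45 x 1.5 = 28.3

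Oxygen-free days carry no highest-value inflation. Averaged over patients, some of whom come off oxygen, the shift against the change in underlying need is about 3 to 25.

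**3. Simulation A.** 100,000 patients per arm; median baseline 4 L/min, exponential decline, zero once flow is below 0.75 L/min, no deaths; k = 3, within-day CV 20%. The 50% event is the first day at the threshold, without the SAP's sustained-success note.

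| Readings | Baseline / study day | Control mean AUC | AUC SD | Arm difference | Power, 20 per arm | Control 50% by Day 14 | Median day |
|---|---|---|---|---|---|---|---|
| Normal | last / highest (SAP) | -11.2 | 35.0 | -10.3 | 16.6% | 63.1% | 10 |
| Normal | highest / highest | -20.9 | 34.9 | -10.3 | 16.4% | 67.3% | 8 |
| Skewed | last / highest (SAP) | -11.3 | 34.8 | -10.3 | 16.6% | 64.1% | 9 |
| Skewed | highest / highest | -20.9 | 36.5 | -10.2 | 14.9% | 68.0% | 8 |
| Skewed | last / last | -17.9 | 31.3 | -8.8 | 15.1% | 67.4% | 8 |

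Over k = 2 to 4 and CV 10% to 30%, matching the baseline rule to the daily rule makes the control mean AUC more negative by about 3 to 19 (largest: -5.2 to -23.9). It raises the 50% rate by about 1 to 8 points. With k = 1 all rules coincide.

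**4. Simulation B.** Baseline mean 6 (SD 2) L/min, fall 0.35 (SD 0.35) L/min per day, s = 1, k = 4, normal readings: mean AUC -13.9 against an underlying -25.4, a shift of 11.5. The 50% reduction is reached by Day 14 in 58%, against 63% with a matched baseline. Extending the settings to k = 2 to 6, s = 0.5 to 1.5 and both shapes gives about 1 to 11 points.

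**5. Variance.** Baseline error enters the AUC as 13 x the SD of the baseline summary. With s = 1, this is 13.0 for one reading. For the highest of three it is 13 x 0.748 = 9.7 if normal, but 13 x sqrt(1 + 1/4 + 1/9) = 15.2 if right-skewed. Under simulation B the ratio of AUC variance, SAP rule to matched rule, is 1.11 with normal and 0.93 with skewed readings, and about 0.86 to 1.23 over 2 to 6 readings. The sign depends on a shape that the documents do not give.

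**The case against.** The strongest reply is that this leaves the treatment comparison untouched. That stands. The choice of baseline summary involves only pre-dose readings, which randomisation balances, so it cannot bias the difference in mean AUC; the simulated difference moves by about 0.1 L/min-days at most. The stricter 50% threshold applies identically to both arms.

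The second reply is that the effect may be small or absent. The highest-value rule is conditional on several readings. It does not act on oxygen-free days or on days given the worst value for death or intubation. The schedule requires only daily recording. This also stands: at one reading a day there is nothing to correct, so it would be wrong to say that every study day is a daily maximum. But the SAP wrote the rule because it expected several readings on some days.

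Third, SAP 5.2 speaks in general terms, so the defect is partly one of specification, and baseline oxygen is already a covariate in SAP 7.2.1.2 and in the Cox model for secondary endpoint 1. Covariate adjustment, however, neither corrects the within-arm AUC means nor redefines the 50% event.

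A reader might also infer that the mismatch adds noise to the primary outcome and costs power. The documents do not support that. The variance ratio falls on either side of 1, and power at 20 per arm changes by at most about 2 points, in either direction.

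**Conclusion.** The concern holds for the within-arm results only. As written, the default baseline and the daily highest-value rule measure different things. With two or more readings a day on oxygen, within-arm improvement is understated and a 50% reduction is harder to reach, under the same rule in both arms. The direction follows from the rules; the size rests on assumptions. For a within-day SD of 0.5 to 1.5 L/min and 2 to 6 readings a day, mean AUC is shifted up by about 3 to 25 L/min-days and 50% reduction by Day 14 is about 1 to 11 points lower. With one reading a day both effects are zero.

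No bias in the between-arm mean difference is claimed, and no gain in precision from the fix. The point merits correction because group means, medians and event rates are what this proof-of-concept trial will report, and the correction is cheap.

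**What to change.** In SAP 5.2, with a cross-reference in 3.2.1 and 3.2.2:

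1. Define baseline oxygen for the primary endpoint and secondary endpoint 1 as the highest flow recorded in the 24 hours before the first dose.
2. State that pre-dose readings do not enter the Day 1 value. Otherwise one reading could serve as both baseline and Day 1, and a patient whose baseline was taken on Day 1 could not show a fall that day.
3. Add a sensitivity analysis with one common summary on both sides, for example the last reading at baseline and on each day.

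The cost is a few sentences and one extra table, using whatever pre-dose readings were recorded. There are two downsides. Patients with a single pre-dose reading keep that value, so some mismatch remains for them; the analysis in item 3 covers them. AUC variance may also rise slightly if within-day readings are right-skewed. If the change comes after the first database lock, SAP section 1 requires it to be documented in the clinical study report.
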